6.1.2 Power calculations for safety

The goal of the safety evaluation for this study is to identify safety concerns associated with vaccine administration. The ability of the study to detect SAEs can be expressed by the true event rate above which at least 1 SAE would likely be observed and the true event rate below which no events would likely be observed. The SAEs will be monitored following each dose. For the first 2 doses, study participants in both groups will receive the same sD-NLT-AB05 + IL-12 DNA adjuvant; thus, the safety sample size can be doubled. Specifically, for this two-arm study with sample size $n = 10$ per group ($n = 20^*$ for safety after the first 2 doses), there is at least a 90% chance of observing at least 1 event if the true rate of such an event is 20.6% (10.9%*) or more and there is at least a 90% chance of observing no events if the true rate is 1.05% (0.53%*) or less. Safety data will be evaluated using historical controls. As a reference, in HVTN vaccine trials conducted in the US from April 2008 through March 2018, about 1% of

participants who received placebos experienced an SAE. Binomial probabilities of observing 0 events, 1 or more events, and 2 or more events among 10 (20*) participants receiving study vaccine are presented in [Table 6-3](#) for a range of possible true AE rates. These calculations provide a more complete picture of the sensitivity of this study design to identify potential safety problems with the vaccine.

Table 6-3 Probability of observing 0 events, 1 or more events, and 2 or more events among a group of 10 (20* for the first two doses) study participants for different true event rates.

True event rate (%)	Group size	0 events	1+ events	2+ events
1	10	0.9	0.1	0
4	10	0.66	0.34	0.06
10	10	0.35	0.65	0.26
20	10	0.11	0.89	0.62
30	10	0.03	0.97	0.85
True event rate (%)	Safety size for the first two doses*	0 events	1+ events	2+ events
1	20*	0.82*	0.18*	0.02*
4	20*	0.44*	0.56*	0.19*
10	20*	0.12*	0.88*	0.61*
20	20*	0.01*	0.99*	0.93*
30	20*	0*	1*	0.99*

An alternative way of describing the statistical properties of the study design is in terms of the 95% CI for the true rate of an AE based on the observed data. [Table 6-4](#) shows the 2-sided 95% confidence intervals for the probability of an event based on a particular observed rate. If none of the 10 (20* for safety after first 2 doses) participants receiving the study vaccine experience a safety event, the 95% 2-sided upper confidence bound for the true rate of such events in the total vaccinated population is 32.6% (19.4%*).

Table 6-4 Two-sided 95% confidence intervals for the probability of observing a safety event based on observing a particular rate of safety endpoints in a group of 10 study participants (n*=20 for safety after first two doses).

Observed event	n	95% CI (%)	
0	10	0	32.6
1	10	0	42.9
2	10	4.9	52.2
3	10	10.6	60.8
Observed event	n*	95% CI (%)	
0	20*	0*	19.4*
1	20*	0*	25.7*
2	20*	1.8*	31.6*
3	20*	4.6*	37.1*

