Overall, the BG505 SOSIP.664 with 3M-052-AF was generally well tolerated, with no unsolicited Grade 3 or 4 AEs, no related SAEs, AESIs, or deaths, and no unplanned study pauses. Other than the persistent erythema in one of the HVTN

137 Part A Group 2 participants described above, all reactogenicity symptoms resolved within 14 days and generally within 7 days. For more detailed information, please see the IB.

HVTN 300 (NCT04915768): This study is a first-in-human, unblinded trial testing a 300 mcg dose of a CH505 TF chTrimer (a stabilized, chimeric SOSIP Env trimer) in combination with a 5 mcg 3M-052-AF + 500 mcg Alum delivered via split injection into both the right and left deltoids. The planned schedule is 5 total vaccinations at months 0, 2, 4, 8, and 12.

As of September 7, 2022, the study is ongoing and all 13 participants have received the first vaccination, 10 participants have received the second vaccination, 9 participants have received the third vaccination, 9 participants have received the fourth vaccination, and 6 participants have received the fifth vaccination. Five participants have discontinued further vaccinations, 1 due to a panic attack after the first injection (this participant had a history of panic attacks before being part of the study), 3 due to reactogenicity events, and 1 was lost to follow-up. Out of these 5, 2 terminated from the study early (panic attack and lost to follow-up) and 3 have remained in the study for follow-up.

All participants experienced at least some local reactogenicity during the trial, mostly mild to moderate. One (1) participant experienced severe pain/tenderness in both the right and left injection sites 3 days following the fourth vaccination, though it lasted only one day.

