6.1.1 Power calculations for immunogenicity

The main goal for the analysis is to evaluate the difference of the frequency and magnitude of HIV-1 specific binding Ab responses, and the rate of CD4+ and CD8+ T-cell responses between the 2 study groups, following the third and fourth vaccination. The precision with which the true response rate can be estimated from the observed data depends on the true underlying response rate and the sample size. Two-sided 95% confidence intervals (CIs) for the response rate based on observing a particular rate of responses in the study groups is shown in [Table 6-1](#). The table indicates n = 9 per group, assuming a 10% loss of data.

Table 6-1 Two-sided 95% CIs for the true response rate based on observing a particular rate of responses in the study groups, n = 9 (total 10 with 10% missing)

N of responses	Observed response rate (%)	95% CI (%)	
0/9	0	0	37.1
1/9	11.1	0.6	49.3
2/9	22.2	3.9	59.8
3/9	33.3	9	69.1
4/9	44.4	15.3	77.3
5/9	55.6	22.7	84.7
6/9	66.7	30.9	91
7/9	77.8	40.2	96.1
8/9	88.9	50.7	99.4
9/9	100	62.9	100

The estimated differences in response rate, as well as their 95% CIs are shown in [Table 6-2](#). Due to the relatively small sample sizes, it is recommended (36) to construct the two-sided response rate difference CIs with Agresti-Caffo interval (37) that is less conservative. The group with higher response rate is assumed to have positive response rate of 50%, 70%, and 90%, and the assumed range of response rate differences between 2 groups is 0% to 50%, 70%, and 90%, respectively. With sample size of 10 for each group, the statistically significant difference in response rates of approximately 50% (44.4%-55.6%) can be detected while controlling Type-I error rate at 5%.

Table 6-2 Observed rate difference between study groups and their two-sided 95% confidence intervals from 10 total study participants per group. Assuming 10% missing rate for immunogenicity endpoints, n = 9 (total 10 with 10% missing).

Group 1 positive response	Group 2 positive response	Observed rate difference (%)	Rate difference 95% CI (%) (Agresti-Caffo)	
5	5	0	-41.6	41.6
5	4	11.1	-32.5	50.7
5	3	22.2	-22.7	59.1
5	2	33.3	-12.2	66.8

Group 1 positive response	Group 2 positive response	Observed rate difference (%)	Rate difference 95% CI (%) (Agresti-Caffo)	
5	1	44.4	-0.9	73.6
5	0	55.6	11.5	79.4
7	7	0	-37.2	37.2
7	6	11.1	-29.6	47.8
7	5	22.2	-21.3	57.7
7	4	33.3	-12.2	66.8
7	3	44.4	-2.4	75.1
7	2	55.6	8.2	82.7
7	1	66.7	19.7	89.4

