6.4 Statistical analyses

This section describes the final study analysis. All data from enrolled participants will be analyzed according to the initial randomization assignment regardless of how many vaccinations they received. The analysis is a modified intent-to-treat analysis in that individuals who are randomized but not enrolled do not contribute data and hence are excluded. Because of the brief length of time between randomization and enrollment—typically no more than 4 working days—very

few such individuals are expected. All analyses will be performed using SAS and R.

No formal multiple comparison adjustments will be employed for multiple safety endpoints, multiple primary immunogenicity endpoints, or secondary endpoints. However, multiplicity adjustments will be made for certain immunogenicity assays, as discussed below, when the assay endpoint is viewed as a collection of hypotheses (eg, testing multiple peptide pools to determine a positive response).

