7.1 Vaccine Regimen

The schedule of vaccination is shown in Section 1 and additional information is given below.

Group 1

Treatment 1 (T1):

INO-6160, 2 mg dose, to be administered as 2 separate intradermal (ID) injections (0.1 mL each) followed by electroporation (EP) using the CELLECTRA 2000 EP device at months 0, 1, 3, and 6.

Group 2

Treatment 2 (T2):

INO-6160, 2 mg dose, to be administered as 2 separate ID injections (0.1 mL each) followed by EP using the CELLECTRA 2000 EP device at months 0, 1, 3 and 6.

Trimer 4571, 100 mcg, admixed with 3M-052-AF, 5 mcg, and Alum, 500 mcg, to be administered as 2 separate intramuscular (IM) injections (0.2 mL each) at months 3 and 6.

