## 8 IMMUNOGENICITY TABLES AND FIGURES, BY ASSAY

If any participants missed the IM administration at Month 3 in Group 2, the analyses of immunogenicity data collected at Visit 7 (2 weeks after the 3rd vaccination) will be done for all participants, and for the subset of participants who received the full Month 0, Month 1 and Month 3 vaccinations in both study groups. If any participants missed the IM administration at Month 6 in Group 2, the analyses of immunogenicity data collected at Visit 9 (2 weeks after the 3rd vaccination) and Visit 10 (6 months after the 4th vaccination) will be done for all participants, and for the subset of participants who received the full Month 0, Month 1, Month 3 and Month 6 vaccinations in both study groups.

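### The n = 10 behind the safety figures for doses 3 and 4 is the most that can be exposed to the Trimer, and the as-randomised, all-visit safety tables would dilute the combination's event rate if anyone in Group 2 misses it

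*Protocol*

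**What the plan says.** **Exposure.** Protocol section 7.1 gives Trimer 4571 with 3M-052-AF and Alum to Group 2 only, "to be administered as 2 separate intramuscular (IM) injections (0.2 mL each) at months 3 and 6". The first two vaccinations are INO-6160 alone in both groups.

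**Safety precision.** Section 6.1.2 says SAEs are monitored after each dose. It uses 20 participants for the first two doses and otherwise 10 per group. For 10 (20) participants it claims "at least a 90% chance of observing at least 1 event if the true rate of such an event is 20.6% (10.9%*) or more", a 90% chance of no event at 1.05% (0.53%) or less, and a two-sided 95% upper bound of 32.6% (19.4%) when no event is seen. It makes no allowance for missed doses.

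**Immunogenicity precision.** Section 6.1.1 does allow for loss: "The table indicates n = 9 per group, assuming a 10% loss of data". Section 6.1 explains this as missing data on the primary immunogenicity endpoints.

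**Analysis rule.** Section 6.4 states: "All data from enrolled participants will be analyzed according to the initial randomization assignment regardless of how many vaccinations they received". Under section 6.4.3, reactogenicity is tabulated by severity and treatment, and each participant enters once per symptom at the worst grade over all vaccinations. AEs are tabulated by severity and relationship. Neither table has a stated denominator for a particular dose.

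**Missed doses.** Sections 5.2.2 and 5.2.3 allow vaccination to be stopped or a dose to be missed. SAP section 8 provides for it ("If any participants missed the IM administration at Month 3 in Group 2", and likewise at Month 6), but only for immunogenicity analyses. Section 1.5 ends replacement at visit 5.

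**The concern.** The adjuvanted Trimer given with INO-6160 is the exposure that distinguishes the two groups, and at most 10 people will have it. Section 6.1.2 describes what can be learned from 10 participants receiving vaccine, while section 6.4 counts everyone randomised. The two agree only if all 10 in Group 2 receive the Trimer.

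The reason given for making no safety allowance, in sections 6.1 and 6.4.3, is that everyone receives at least one vaccination. That first vaccination contains no Trimer, so the reason does not cover the combination.

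At stake is the reported event rate. Keeping unexposed people in the denominator lowers the rate of events that follow the Trimer, which for safety is the unfavourable direction. Pooling over all visits adds a second blur: a worst grade reached after an INO-6160-only dose looks the same in the table as one reached after the combination.

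**Working it through.** **Step 1: reproduce the printed figures.** Inputs are n = 10 and n = 20 from section 6.1.2.

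- Rate at which at least one event is seen with 90% probability: 1 − 0.1^(1/n). n = 10: 20.6%. n = 20: 10.9%.
- Rate at which no event is seen with 90% probability: 1 − 0.9^(1/n). n = 10: 1.05%. n = 20: 0.53%.
- Upper 95% bound with 0 events, adding two successes and two failures: p = 2/(n + 4), bound = p + 1.96 × √[p(1 − p)/(n + 4)]. n = 10: p = 2/14 = 0.1429, bound = 0.1429 + 1.96 × 0.0935 = 32.6%. n = 20: p = 2/24 = 0.0833, bound = 0.0833 + 1.96 × 0.0564 = 19.4%.

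All agree with the protocol, and Tables 6-3 and 6-4 also reproduce. There is no arithmetic error.

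**Step 2: can the exposed number fall below 10?** Appendices A and B put visit 5 at day 43 and vaccination 3 at day 85. A participant lost between those days cannot be replaced. Replacement of earlier losses was possible, with up to 5 extra participants, but SAP section 4 reports exactly 10 + 10 enrolled. So 10 is the ceiling, and the documents give no rate from which to predict the shortfall.

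**Step 3: the same formulas with fewer exposed.** The rows for 9 and 8 are assumptions for illustration.

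| Exposed | ≥1 event with 90% probability | No event with 90% probability | Upper bound, 0 events | Chance of ≥1 event at a true 20.6% |
|---|---|---|---|---|
| 10 (printed) | 20.6% | 1.05% | 32.6% | 90.0% |
| 9 | 22.6% | 1.16% | 35.0% | 87.5% |
| 8 | 25.0% | 1.31% | 37.8% | 84.2% |

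**Step 4: dilution under the section 6.4 rule.** Let m of 10 receive the Trimer, and suppose the event in question occurs only after it. Then the as-randomised rate is the rate among the exposed × m/10, a factor of 0.9 for m = 9 and 0.8 for m = 8. For example, 4 events among 8 exposed is 4/8 = 50%, but is reported as 4/10 = 40%.

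**The case against.** The best defence is that section 6.1.2 is right as written. Its figures are stated for participants receiving vaccine, they reproduce exactly, and Table 6-3 already shows a range of event rates. That stands.

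A reader might go further and infer that 20.6% and 32.6% are wrong and should be replaced by values for n = 9, or worse. The documents do not support this, for two reasons.

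- The 10% in sections 6.1 and 6.1.1 is missing assay data, including problems with samples. It is not a rate of missed vaccination, so using 9 in one place and 10 in the other is not a contradiction.
- Section 2.4 reports of the HVTN 300 trial, which used the same adjuvant doses, that "Five participants have discontinued further vaccinations" out of 13. But all 13 had received a first adjuvanted dose, and 3 of the 5 stopped for reactogenicity. Those people belong in a safety denominator. That trial also used a different trimer at 300 mcg on a five-dose schedule. It may bear on who receives a second Trimer dose, but not on who never receives one.

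Loss before the Trimer would occur during INO-6160 dosing. The four DNA trials in Table 2-1 list 1, 2, 3 and 1 discontinuations for adverse events, pain or similar reasons among 120, 48, 100 and 94 participants: 7/362, about 2%. Other reasons for loss are not tabulated there, so 2% is not the whole rate, but it gives no support for assuming heavy loss.

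It can also be said that the effect is small. The exact upper bound is 30.8% at n = 10 and 33.6% at n = 9, so the printed 32.6% is only 1 point below the exact value with one participant lost. Pause rules act on single events, and enrolment is complete. These points reduce the weight of the restated figures, but they do not answer the denominator problem. The per-participant AE listing in section 6.4.3 lets a reader reconstruct exposure, but a listing does not replace a correctly based rate.

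**Conclusion.** The point holds as a cheap improvement. It is not an arithmetic error, and the 10% and the 5 of 13 should not be used as rates of never receiving the Trimer.

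The main part is the stated analysis rule. As-randomised analysis whatever doses were received, with reactogenicity pooled over all visits, leaves any unexposed Group 2 participant in the combination's denominator and multiplies its rate by m/10. The SAP does not correct this: by its sections 1 and 7.1 it covers immunogenicity, and its subset rule in section 8 is limited to that.

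The lesser part is that n = 10 is a ceiling. One fewer exposed moves 20.6% to 22.6% and 32.6% to 35.0%; two fewer move them to 25.0% and 37.8%.

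All this depends on at least one Group 2 participant not receiving the Trimer. If all 10 receive it at both visits, the received and randomised denominators coincide and only the pooling over visits remains. A separate safety analysis document, if one exists, might already settle the denominator; these two documents do not.

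**What to change.** **Section 6.4.3.** Add tables of reactogenicity and AEs after dose 3 and after dose 4. The denominator is participants who received that dose, grouped by product actually received (INO-6160 alone, or INO-6160 with adjuvanted Trimer 4571). Print them beside the as-randomised, all-visit summary. Keep as-randomised analysis for immunogenicity.

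**Section 6.1.2.** State that n = 10 is the maximum exposed to the Trimer. Beside it show, labelled as assumptions, n = 9 (22.6% / 1.16% / 35.0%) and n = 8 (25.0% / 1.31% / 37.8%).

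**Cost.** One extra set of tables and a few sentences. The received-dose groups are not protected by randomisation and may favour people who tolerated earlier doses, which is why the as-randomised summary should stay. The quoted sensitivity becomes slightly less favourable.

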3.1 Primary objectives and endpoints

Objectives	Endpoints
1. To evaluate the safety and tolerability of 2 doses of sD-NLT-AB05 + IL-12 DNA adjuvant followed by 2 doses of sD-NLT-AB05 + IL-12 DNA adjuvant alone or in combination with Trimer 4571 adjuvanted with 3M-052-AF + Alum	a) Local and systemic reactogenicity signs and symptoms will be collected for a minimum of 2 weeks following receipt of any study vaccine b) Serious adverse events (SAEs), medically attended adverse events (MAAEs), adverse events of special interest (AESIs) and AEs leading to early participant withdrawal or permanent discontinuation will be collected throughout the study and for 12 months following any receipt of study product. Additionally, all adverse events will be collected for 30 days after any receipt of study vaccination.
2. To evaluate the immunogenicity of 2 doses of sD-NLT-AB05 + IL-12 DNA adjuvant followed by 2 doses of sD-NLT-AB05 + IL-12 DNA adjuvant alone or in combination with Trimer 4571 adjuvanted with 3M-052-AF + Alum	a) Response rate and magnitude of vaccine-matched IgG binding Ab responses as assessed by multiplex assay 2 weeks following the fourth vaccination b) Response rate and magnitude of CD4+ and CD8+ T-cell responses measured by flow cytometry, to HIV-1-specific Env peptide pools, 2 weeks following the fourth vaccination

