6.4.3 Safety/tolerability analysis

Since enrollment is concurrent with receiving the first vaccination, all participants will have received at least 1 vaccination and therefore will provide some safety data.

Reactogenicity: The number and percentage of participants experiencing each type of reactogenicity sign or symptom will be tabulated by severity and treatment. For a given sign or symptom, each participant's reactogenicity will be counted once under the maximum severity for all injection visits. Wilcoxon rank sum tests will be used to test for differences in severity between groups.

AEs and SAEs: AEs will be coded into Medical Dictionary for Regulatory Activities (MedDRA)–preferred terms. The number and percentage of participants experiencing each specific AE will be tabulated by severity and relationship to study vaccine. For the calculations in these tables, each subject's AE will be counted once under the maximum severity or strongest recorded causal relationship to treatment. A complete listing of AEs for each subject will provide details including severity, relationship to treatment, onset, duration, and outcome.

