6.4.4.2 General approach for secondary and exploratory analyses

For the statistical analysis of immunogenicity endpoints, data from enrolled participants will be used according to the initial randomization assignment regardless of how many injections they received. Additional analyses may be performed, limited to participants who received all scheduled injections per protocol. Assay results that are unreliable, from specimens collected outside of the visit window, or from HIV-infected participants are excluded. Since the exact date of HIV infection is unknown, any assay data from blood draws 4 weeks, or less, prior to an infected participant's last seronegative sample and thereafter may be excluded. If an HIV-infected participant does not have a seronegative sample post enrollment, then all data from that participant may be excluded from the analysis.

Discrete categorical assay endpoints (eg, response rates) will be analyzed by tabulating the frequency of positive response for each assay by antigen and treatment arm at each timepoint for which an assessment is performed. Crude response rates will be presented with their corresponding 95% CI estimates calculated using the score test method (38). Fisher's exact tests will be used to compare the response rates of between 2 vaccine groups, with a significant difference declared if the 2-sided p-value is ≤ 0.05 .

For quantitative assay data (eg, magnitude of HIV-1 Env-specific binding Ab responses), graphical and tabular summaries of the distributions by antigen, treatment arm, and timepoint will be made. The difference between arms at a specific timepoint will be tested with a nonparametric Wilcoxon rank sum test if

the data are not normally distributed and with a 2-sample t-test if the data appear to be normally distributed. An appropriate data transformation (eg, log10 transformation) may be applied to better satisfy assumptions of symmetry and homoscedasticity (constant variance). More sophisticated analyses employing repeated measures methodology (for example, repeated measures analysis of variance or generalized estimating equations) may be utilized to incorporate immune responses over several timepoints and to test for differences over time. However, inference from such analyses would be limited by the small sample size of this study. All statistical tests will be 2-sided and will be considered statistically significant if $p \leq 0.05$.

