## 1 OVERVIEW

The following describes the Statistical Analysis Plan (SAP) for the analysis of immunogenicity data from HVTN 304 for Protocol Team (PT) reports of immunogenicity data, and for the Final Study Report (FSR) of Immunogenicity.

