### 7.1 Analysis Variables

The analysis variables consist of baseline participant characteristic, and immunogenicity for primary- and secondary-objective analyses.

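### Does the unspecified comparison with historical controls, with Table 6-4's interval unnamed, leave the safety conclusion open?

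*Protocol*

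**What the plan says.** Safety and tolerability form the first primary objective (Protocol 3.1: "To evaluate the safety and tolerability of 2 doses of sD-NLT-AB05 + IL-12 DNA adjuvant").

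Protocol 6.1.2 describes what 10 participants per group, or 20 pooled for the first two doses, can reveal about event rates. It then says: "Safety data will be evaluated using historical controls. As a reference, in HVTN vaccine trials conducted in the US", and gives about 1% SAEs in placebo recipients (April 2008 to March 2018). Table 6-4 follows as another way to describe the design: "Two-sided 95% confidence intervals for the probability of observing a safety event based on observing a particular rate of safety endpoints". It prints 0% to 32.6% for 0/10 and 0% to 42.9% for 1/10, and does not name the method.

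The planned analysis is in Protocol 6.4.3. For adverse events it reads: "The number and percentage of participants experiencing each specific AE will be tabulated by severity and relationship to study vaccine". A complete listing per participant is added, and reactogenicity severity is compared between groups by a rank sum test. No safety interval and no historical comparison appear there.

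The SAP does not take this up. Its scope is the "Statistical Analysis Plan (SAP) for the analysis of immunogenicity data from HVTN 304", and under SAP 7.1 "The analysis variables consist of baseline participant characteristic, and immunogenicity for primary- and secondary-objective analyses".

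The only one-sample interval method named is in Protocol 6.4.4.2, repeated in SAP 7.2, and it concerns immunogenicity: "Crude response rates will be presented with their corresponding 95% CI estimates calculated using the score test method".

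**The concern.** A comparison is announced for a primary objective and the analysis section does not carry it out. The protocol also shows or names three kinds of one-sample interval: one in Table 6-4, another in Table 6-1, and the score method in 6.4.4.2. None is assigned to the safety analysis.

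With 10 per arm, a single SAE is a realistic outcome. Table 6-3 puts the chance of one or more at 0.10 if the true rate is 1% and at 0.65 if it is 10%. If the report then said whether the observed rate was compatible with the historical 1%, the answer could depend on which interval the analyst picked after seeing the count. Table 6-4 also prints a lower limit of 0% for 1/10 and 1/20, although a rate of zero is impossible once an event has occurred. That can look like an error.

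**Working it through.** **Inputs.** n = 10 per group and 20 pooled (6.1.2); reference rate about 1% (6.1.2); two-sided 95%, so z = 1.96; Tables 6-1, 6-3 and 6-4.

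**Step 1: reproduce Table 6-4.** Adjusted Wald: p̃ = (x + 2)/(n + 4); limits p̃ ± 1.96·√[p̃(1 − p̃)/(n + 4)], with negative values set to 0.

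- 0/10: p̃ = 2/14 = 0.1429; half-width 1.96·√(0.1429·0.8571/14) = 0.1833; upper limit 32.6%.
- 1/10: p̃ = 3/14 = 0.2143; half-width 1.96·√(0.2143·0.7857/14) = 0.2149; limits −0.07% and 42.9%.

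| Events | n = 10, computed % | Printed | n = 20, computed % | Printed |
|---|---|---|---|---|
| 0 | −4.04 to 32.62 | 0 to 32.6 | −2.72 to 19.39 | 0 to 19.4 |
| 1 | −0.07 to 42.92 | 0 to 42.9 | −0.73 to 25.73 | 0 to 25.7 |
| 2 | 4.91 to 52.24 | 4.9 to 52.2 | 1.76 to 31.58 | 1.8 to 31.6 |
| 3 | 10.61 to 60.81 | 10.6 to 60.8 | 4.59 to 37.08 | 4.6 to 37.1 |

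All eight rows match. The 0% lower limits at 1/10 and 1/20 are truncated from −0.07% and −0.73%. Other methods do not fit: at 0/10 the upper limit would be 27.7% (score), 34.5% (continuity-corrected score) or 30.8% (exact).

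**Step 2: Table 6-1.** The continuity-corrected score interval reproduces its ten rows to within 0.1 point; for example, 1/9 gives 0.58% to 49.33% against the printed 0.6% to 49.3%.

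**Step 3: lower limits near 1%.** Score interval at 1/10: centre (0.1 + 3.84/20)/(1 + 3.84/10) = 0.2110; half-width (1.96/1.384)·√(0.1·0.9/10 + 3.84/400) = 0.1931; limits 1.79% and 40.4%. Exact lower limit at 1/10: 1 − 0.975^(1/10) = 0.25%.

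| Lower limit, % | 1/10 | 2/10 | 1/20 | 2/20 |
|---|---|---|---|---|
| Adjusted Wald (Table 6-4) | 0 (−0.07) | 4.91 | 0 (−0.73) | 1.76 |
| Score (named for immunogenicity) | 1.79 | 5.67 | 0.89 | 2.79 |
| Continuity-corrected score (Table 6-1 type) | 0.52 | 3.54 | 0.26 | 1.75 |
| Exact | 0.25 | 2.52 | 0.13 | 1.23 |

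Against 1%, the methods differ only at 1/10, and there only the score interval stands apart. All four include 1% at 1/20, and all four exclude it at 2/10 and 2/20.

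**Step 4: what would hang on it, if exclusion of 1% were a rule.** With n = 10, P(1 or more) = 1 − (1 − p)^10 and P(2 or more) = 1 − (1 − p)^10 − 10p(1 − p)^9.

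| True rate | Score (needs 1 or more) | Other three (need 2 or more) |
|---|---|---|
| 1% | 0.096 | 0.004 |
| 10% | 0.65 | 0.26 |
| 20% | 0.89 | 0.62 |

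These figures agree with Table 6-3 where it covers the same rates. They describe a rule that neither document contains.

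**Step 5: compare with the plan.** The contrast in Step 4 needs two things: the score method applied to safety, and a decision tied to excluding 1%. Sections 6.4.4.2 and SAP 7.2 confine the score method to immunogenicity response rates. Section 6.1.2 calls the 1% a reference and sets no test, threshold or decision rule.

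**The case for a change.** The strongest case for a change is that section 6.1.2 commits to an evaluation, that nothing assigns an interval to safety, and that nothing prevents an analyst from carrying the score method over. The disagreement at 1/10 also does not depend on reading the reference as exactly 1%. Table 6-4's method and the score method part ways there at every reference rate checked from 0.5% to 1.7%. At n = 20 the score interval would also stand apart for a reference below its 0.89% lower limit. The remedy would be a sentence or two and a caption.

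The arithmetic in that case stands, and so does the missing description. The consequence does not. The only safety interval in the plan is Table 6-4, which prints the disputed result, 1/10, in advance as 0% to 42.9%. An analyst who reported a score interval instead would be departing from the one safety table the protocol gives. The method can also be traced: section 6.1.1 cites the source of the Agresti-Caffo interval, and the title of that reference covers single proportions and the device of adding two successes and two failures. If Table 6-4 is read purely as a design illustration, then no safety interval is planned at all, and the scope for choosing one to suit the data shrinks further. Since the SAP is expressly limited to immunogenicity, its silence on safety does not show that safety reporting is unplanned elsewhere.

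**Conclusion.** No change is needed. The gap is real but descriptive. Table 6-4 is correct for its method in all eight rows, and cutting a negative limit at zero is ordinary practice. The conflict over 1% is confined, at that reference, to exactly one event in an arm of 10. It arises only under an exclusion rule the plan does not state, using an interval the plan reserves for other endpoints.

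Followed as written, the plan gives a sound account of safety in 20 people: counts and percentages by severity and relationship, a listing of every event, and a background rate for context. Safety action does not wait on an interval. Under Table 9-1 any related SAE leads to an immediate pause and review by the Protocol Safety Review Team, and the Safety Monitoring Board reviews the data about every four months. An analyst would sensibly treat the 1% as context. Calling the comparison descriptive, labelling the table or noting the truncation would be harmless tidying and would change no printed figure.

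This rests on two assumptions: that the 1% is used as the reference the protocol calls it, and that no claim of excess risk is built on an interval excluding it. If such a claim were planned, the interval would have to be named beforehand.
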